#### (2) Learning phase

The experimental procedure followed the classic retrieval practice paradigm, which included a learning phase and a final test phase.

During the experiment, participants were informed that they would learn two lists of

words. Subsequently, they might either learn the words again or complete a list recall test, and will be given a final test shortly thereafter. The learning of the retrieval practice list and the restudy list was conducted in a randomly balanced manner. Each word was presented for 5 seconds, with a 500-millisecond interval between words. To avoid providing secondary retrieval cues between examples, all words were shuffled pseudo-randomly within categories. Each list contained 17 words, consisting of 5 examples from each of the 3 experimental categories (15 experimental examples, 2 filler examples). The first and last words presented in each list were filler words, thus controlling for the primacy and recency effects on memory.

For the retrieval practice list, participants underwent two learning sessions and two retrieval sessions (S-T-S-T). During retrieval, participants were instructed to write down all the words they had just remembered within 5 minutes. For the restudy list, participants underwent four study sessions (S-S-S). Between each learning cycle, participants completed a 3-minute simple arithmetic task (dispersed attention task).

(3) Testing phase

Immediate Test: Participants were instructed to recall as many words as possible from the learned lists within 10 minutes after completing all learning tasks.

Delayed Test: Participants were informed to recall as many words as possible from the

learned lists within 10 minutes 24 hours later.

Figure 1. Experiment procedure.

#### 2.5 Date scoring & analysis

The experimental results were processed using SPSS 26.0. The correct recall rate of word lists was calculated for each subject by the experimental assistant. Then, Free recall organization was measured by the Adjusted Ratio of Clustering (ARC) scores [14,15]. ARC scores range from 1 to 1. A 0 score indicates a level of clustering similar to what would be expected by chance, and a score of 1 implies perfect clustering. Negative values of ARC scores mean atypical and uninterpretable recall patterns[16]. For that reason, negative scores were excluded from analyses.

A mixed-design analysis of variance (ANOVA) was conducted to compare the correct recall rates and ARC clustering scores between the two learning strategies under two stimulation conditions. All statistical tests were performed at a significance level of 0.05, and post-hoc comparisons were adjusted using Bonferroni correction. Effect sizes were reported using partial eta-squared ( $\eta_p^2$ ; ANOVAs).

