#### 2.2 Design

A mixed experimental design of 3 (Stimulation type: tES stimulation, tACS stimulation, sham stimulation)  $\times$  2 (Learning strategy: retrieval practice, restudy)  $\times$  2 (Retention interval: Immediate recall, Delayed recall) was employed. Stimulation type was a between-subjects variable, while learning strategy and testing time were within-subject variables. The dependent variables were the correct recall rate and Adjusted Ratio of Clustering (ARC) scores in the testing phase.

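### On a list of three categories of five words, ARC is undefined or all-or-nothing at very low recall, and dropping negative scores then makes poor recallers look perfectly organised

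*Protocol*

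**What the plan says.** Protocol section 2.2 makes ARC one of two outcomes: "The dependent variables were the correct recall rate and Adjusted Ratio of Clustering (ARC) scores in the testing phase". The same section fixes the repeated measures: "Stimulation type was a between-subjects variable, while learning strategy and testing time were within-subject variables". Each patient therefore contributes 2 x 2 = 4 ARC scores.

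Section 2.4, under the learning phase, fixes the list: "Each list contained 17 words, consisting of 5 examples from each of the 3 experimental categories (15 experimental examples, 2 filler examples".

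Section 2.5 gives the range, "ARC scores range from 1 to 1", where a minus sign was probably lost when the text was extracted. It gives the anchors, "A 0 score indicates a level of clustering similar to what would be expected by chance, and a score of 1 implies perfect clustering". It calls negative values uninterpretable and continues: "For that reason, negative scores were excluded from analyses". The scores then enter the model: "A mixed-design analysis of variance (ANOVA) was conducted to compare the correct recall rates and ARC clustering scores between the two learning strategies".

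The protocol does not mention that the score can fail to exist, sets no minimum recall for scoring, and states no expected recall level.

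**The concern.** A score scaled to 0 at chance and 1 at perfect clustering divides by the distance between chance and the maximum. With few recalled words that distance can be zero, or so small that only extreme values are possible. Low recall is most plausible in memory-impaired patients tested 24 hours later, and retention is what the trial wants to influence.

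Two things are at stake. First, some cells have no score, and which cells these are depends on recall, the other outcome. A standard mixed ANOVA that needs all four cells would then favour better recallers. Second, once negatives are removed, the score expected from a patient with no organisation at all rises as recall falls. Any difference in recall between strategies, intervals or arms would then create a difference in ARC that has nothing to do with organisation.

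**Working it through.** **Inputs.** Three categories of five words per list (section 2.4, learning phase); anchors and exclusion of negatives (section 2.5); four cells per patient (section 2.2). Recall level: not stated, so varied below.

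**Formula.** The anchors imply ARC = (R - E)/(max - E). R is the number of adjacent same-category pairs, E = sum(n_i^2)/N - 1, and max = N - k, for N recalled words from k categories with n_i in each. Enumerating every recall order confirmed that E is the chance mean for every category pattern.

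**When it is undefined.** max = E when all recalled words share one category, or when each comes from a different category. That covers every recall of one or two words. On one list it can also happen at three to five words, but not from six upward.

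**Three words.** There are 455 possible sets.
- All one category: 3 x 10 = 30. All different: 5^3 = 125. Undefined: 155/455 = 34.1%.
- The remaining 300 have pattern (2,1): E = 5/3 - 1 = 2/3, max = 1. With the pair adjacent (probability 2/3), ARC = (1/3)/(1/3) = +1. Otherwise ARC = (-2/3)/(1/3) = -2.
- Mean: (2/3)(1) + (1/3)(-2) = 0. SD: sqrt(2/3 + 4/3) = 1.41.
- After negatives are dropped, every retained score is 1.

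**Four words.** There are 1,365 sets.
- (4): 15 sets, 1.1%, undefined.
- (3,1): 300 sets, ARC +1 or -1, each with probability 1/2.
- (2,2): 300 sets, ARC +1, 0 or -1, each 1/3.
- (2,1,1): 750 sets, ARC +1 or -1, each 1/2.
- Overall: +1 in (150 + 100 + 375)/1365 = 45.8%, 0 in 7.3%, -1 in 45.8%. Mean retained: 0.458/(0.458 + 0.073) = 0.86.

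**Other recall counts**, by the same exact enumeration (random words, random order):

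| Words recalled | Undefined | Score exactly 1 | Negative | Chance SD, negatives kept | Mean after dropping negatives |
|---|---|---|---|---|---|
| 1 or 2 | 100% | - | - | - | - |
| 3 | 34.1% | 44.0% | 22.0% | 1.41 | 1.00 |
| 4 | 1.1% | 45.8% | 45.8% | 0.96 | 0.86 |
| 5 | 0.1% | 23.5% | 50.4% | 0.67 | 0.58 |
| 8 | 0% | 1.6% | 44.9% | 0.37 | 0.27 |
| 15 | 0% | under 0.1% | 39.9% | 0.21 | 0.14 |

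With negatives kept, the chance mean of the defined scores is 0 at every count from 3 to 15.

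**Stated range.** The upper limit of 1 is right. A lower limit of -1, if that was meant, is not: (2,1) reaches -2. Pattern (3,1,1) has E = 11/5 - 1 = 1.2 and max = 2, so with R = 0, ARC = -1.2/0.8 = -1.5.

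**How often, under an assumption.** Suppose each of the 15 words is recalled independently with the same probability, in chance order. A cell with no recall counts as undefined. The last column also assumes that the four cells are independent.

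| Assumed recall | Undefined cells | All four cells defined |
|---|---|---|
| 20% | 49% | 7% |
| 30% | 19% | 44% |
| 40% | 5% | 81% |
| 50% | 1% | 97% |

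If both lists were scored together as six categories, undefined scores would be more frequent: 63% at three words and 34% at four.

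**The case against.** The strongest reply is that ARC is itself centred on chance. With negatives kept it averages 0 at every recall count, so the upward shift at low recall is produced by the exclusion. This stands. A reader might infer that ARC on its own inflates organisation in poor recallers, or that this fault is separate from the handling of negatives. The protocol's figures do not support either reading. Apart from the exclusion, what remains is the undefined cells and the unequal spread.

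Second, undefined scores are confined to very low recall: about 1% at four words and negligible from five. Patients must be stable and able to complete the tasks, and each list is presented repeatedly. A reader might infer that the endpoint will fail in many patients. The protocol gives no recall level, so that is possible but not shown.

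Third, a minimum count and a missing-cell rule could sit in an analysis plan that is not available here, and the protocol does not say that a patient with one missing cell is dropped. That is fair, and the absence of such rules is not the point. The point is that the score, list and exclusion already fixed in the protocol give a wrong result at low recall.

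Fourth, the range statement changes no analysed score, because every retained value lies between 0 and 1. This also stands; it is a wording correction.

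Finally, replacing ARC by R - E(R) would bring its own confounding. The ceiling of that difference averages 0.6 at four words, 3.0 at eight and 8.0 at fifteen, so it rises with recall at the same degree of clustering. It should not become the main score.

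**Conclusion.** The point holds in this limited form. On a 3 x 5 list, ARC does not exist at one or two recalled words or in 34% of random three-word recalls, and at three words it is otherwise +1 or -2. Combined with the stated exclusion of negatives, patients with no organisation have a mean retained score of 1.00 at three words, 0.86 at four, 0.27 at eight and 0.14 at fifteen. The dependence on recall is therefore not confined to the lowest counts, and it belongs jointly to the score and the exclusion. Removing the exclusion alone would leave the undefined cells and a chance SD falling from 1.41 at three words to 0.37 at eight.

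The per-count figures are exact for random words in random order, scored per list. The share of patients affected rests on recall levels that the protocol does not give: undefined cells run from about 49% at 20% recall to about 1% at 50%. The change should be made before recruitment, but the documents do not show that the ARC analysis is bound to fail.

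**What to change.** In section 2.5:

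- Keep ARC as the organisation measure, but analyse it only in cells that reach a minimum recall count fixed in advance, for example five or more experimental words.
- Keep negative scores in those cells, so that chance ordering averages 0. This replaces the current exclusion and should be settled in the same amendment.
- Report the number of undefined and below-minimum cells by arm, strategy and interval. At five words a single-category recall is still undefined (0.1% under random recall), so the undefined category is still needed.
- Add R - E(R) as a sensitivity analysis only. It is defined whenever at least one word is recalled and averages 0 at chance, but its maximum grows with recall.
- Restate the range as at most 1, with a lower limit that depends on the words recalled and can lie below -1.

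The cost is protocol wording and a second formula on the same recall sheets; no new data are needed, and the protocol lists the study as not yet recruiting. The downside is that some low-recall cells leave the ARC analysis, so its conclusions apply to patients who recall enough words to show organisation.

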A study involving 119 healthy subjects investigated the combination of tES intervention with retrieval practice and found that the strong retrieval practice effect left no room for tES to improve memory performance[7]. The combination of single-session online tES with retrieval practice in healthy individuals and found that the memory performance of anodal stimulation was inferior to cathodal stimulation and sham stimulation [8]. We have already explored the role of continuous periodic tES combined with interim testing on spatial route learning in patients with schizophrenia in a previous study [9], and found that both the learning strategy and tES independently facilitated the ability of patients with schizophrenia to learn new information in spatial route learning, suggesting that the tES of L-DLPFC has a significant improvement effect. In contrast, targeted tES treatment may be more effective for memoryimpaired populations such as schizophrenia [10]. Therefore, further investigation is needed to determine the effectiveness of combining tES and retrieval practice for semantic memory intervention in schizophrenia patients. From a theoretical perspective, this combination may have a dual activation effect because (1) tES stimulation can enhance activation levels of the L-DLPFC, improving its cognitive function impairment; (2) retrieval practice can not only help patients initiate semantic memory strategies and promote semantic elaboration but also actively activate the brain regions stimulated by tES, thereby producing a synergistic effect.

Therefore, this study aims to investigate whether combining tDCS, tACS with retrieval practice facilitates the maintenance of semantic memory and improvement of semantic organization by comparing the use of retrieval practice strategies in patients receiving anodal L-DLPFC stimulation, sham stimulation.

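### Dropping every negative ARC score truncates an outcome whose chance level is 0; this biases ARC upward and can hide or reverse the strategy and delay contrasts

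*Protocol*

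**What the plan says.** Section 2.5 defines the scale by its chance level: "A 0 score indicates a level of clustering similar to what would be expected by chance". It then states that "Negative values of ARC scores mean atypical and uninterpretable recall patterns", citing a source, and concludes: "For that reason, negative scores were excluded from analyses". No threshold, expected number of exclusions or analysis with the scores kept is given. The section does not say whether a negative value removes one score or the whole patient.

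ARC is not a side measure. Section 2.2 reads: "The dependent variables were the correct recall rate and Adjusted Ratio of Clustering (ARC) scores in the testing phase". Each patient contributes four scores: two learning strategies at two tests ("Retention interval: Immediate recall, Delayed recall"). Section 2.5 uses a mixed-design ANOVA to "compare the correct recall rates and ARC clustering scores between the two learning strategies". The Introduction asks whether the combined intervention "facilitates the maintenance of semantic memory and improvement of semantic organization", and ARC is the only measure of organization.

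**The concern.** The statements in section 2.5 do not fit together. If 0 is chance, a score slightly below 0 is the ordinary result of weak or absent clustering, and is as interpretable as one slightly above 0. Excluding all negative values selects patients or cells on the outcome itself, and both stimulation and strategy may influence that outcome.

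A uniform upward shift would do limited harm to contrasts, but this shift is not uniform. ARC is noisier when few words are recalled, so the lower tail is larger and its removal lifts the mean further. Three consequences follow:

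- If retrieval practice raises recall, restudy ARC is inflated more, and a real benefit can vanish or reverse.
- If recall falls over 24 hours, delayed ARC is inflated more, and a real loss of organization can look like maintenance.
- If the repeated-measures ANOVA drops incomplete cases, one negative value among four removes the patient.

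**Working it through.** The protocol gives no figure to reproduce, so the rule's effect was computed from the list structure.

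**Inputs from the protocol.** Each list holds 15 experimental words ("consisting of 5 examples from each of the 3 experimental categories", Learning phase); 60 patients (section 2.1); four ARC scores per patient (section 2.2); significance level 0.05 (section 2.5).

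**Assumptions.** ARC is scored per list, because section 2.5 compares it between strategies. Words recalled range from 5 to 12 of 15. Clustering is set by s, the probability that the next word is deliberately taken from the same category (s = 0 is chance).

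**Formula.** ARC = (R − E) / (maxR − E), where R is the number of within-category repetitions, E = Σnᵢ²/N − 1, and maxR = N − k for N words recalled from k categories.

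**Exact small case.** Take 6 words recalled, 2 from each category. E = (4+4+4)/6 − 1 = 1 and maxR = 6 − 3 = 3. Of the 90 possible category orders, 30 have R = 0 (ARC −0.5), 36 have R = 1 (ARC 0), 18 have R = 2 (ARC 0.5) and 6 have R = 3 (ARC 1). The mean in random order is (−15 + 0 + 9 + 6)/90 = 0, as the protocol says. After the negatives are dropped it is (9 + 6)/60 = 0.25.

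**Simulation over all compositions, 5 to 12 words:**

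| Clustering | True mean ARC | Negative share | Mean after exclusion |
|---|---|---|---|
| Chance (s = 0) | 0 | 44–54% | 0.57 (5 words) to 0.21 (12 words) |
| Weak (s = 0.2) | about 0.22 | 23–37% | 0.65 (5 words) to 0.33 (12 words) |
| Strong (s = 0.7) | about 0.7 | 0.2–11% | raised by 0.13 at 5 words, by about 0.01 or less at 8 or more |

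**Strategy contrast, true benefit.** At 9 words and s = 0.4 the mean goes from 0.439 to 0.513. At 6 words and s = 0.2 it goes from 0.212 to 0.503. The true gap, 0.439 − 0.212 = 0.227, becomes 0.513 − 0.503 = 0.010. Power with 60 patients falls from 97% to 5–6%. At 8 words in both conditions, +0.21 becomes +0.13 and power falls from 99% to 60–81%. With strong clustering at 12 against 10 words, +0.21 becomes +0.18 with no loss of power.

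**Strategy contrast, no true difference** (60 patients, 9 against 6 words; share of significant results):

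| s | All scores | Single scores dropped | Incomplete patients dropped |
|---|---|---|---|
| 0.2 | 4.3% | 61% | 28% |
| 0.4 | 5.3% | 52% | 38% |
| 0.7 | 6.9% | 12% | 12% |

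Under exclusion the rate is 5–6% at 8 against 8 words and 5–11% at 12 against 10.

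**Delay contrast.** From 9 words at s = 0.4 to 6 words at s = 0.3, a true loss of 0.12 appears as a gain of 0.05.

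**Stimulation contrast**, assuming 20 per arm in three equal arms and 8 words recalled in both arms. For s = 0.4 against 0.2, power is 92% with all scores, 66% with single scores dropped and 40% with incomplete patients dropped. For s = 0.7 against 0.5 it is 97%, 91% and 89%.

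**Patients kept if all four scores are required.** With independent cells the share is (1 − negative share)⁴. At weak clustering, 0.77⁴ = 0.35 and 0.63⁴ = 0.16, or about 21 down to 9 of 60. Under perfect dependence the share is 0.77 down to 0.63, or about 46 to 38 of 60. With correlated cells (patient SD of 1 on the logit of s, 6 to 10 words), 60–74% of patients have at least one negative score at a mean ARC of 0.26, and 9–26% at 0.70.

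**The case against.** The size of the harm depends on recall and clustering levels that the protocol does not give, and some features point to the mild end. The categories are common and distinct, category–word relevance was rated 4.65 to 4.75 out of 5 (section 2.3.2), each list is presented repeatedly, and the pseudo-random shuffling within categories can be read as blocked presentation, which would raise clustering. With strong clustering and 8 or more words, hardly any scores are negative. This stands as a limit on size. It does not defend the rule, because patients chosen for a semantic memory deficit may cluster weakly, and the rule improves the analysis in none of the settings examined.

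Three further limits stand:

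- Patient loss depends on how the ANOVA treats a missing cell, which is not stated.
- Attenuation of a stimulation effect was shown only for equal recall in the arms; unequal recall could move it either way.
- If ARC were scored over both lists together, about half of scores would still be negative at chance, but 13–24% at an ARC of about 0.2 and under 1% at about 0.7. Joint scoring fits poorly with comparing ARC between strategies.

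The protocol does cite a source for calling negative values uninterpretable. A citation does not remove the conflict with the protocol's own statement that 0 is chance.

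**Conclusion.** The rule is wrong as written and should be changed before data are collected. Upward bias is certain whenever a negative score occurs. Hidden or reversed strategy and delay contrasts follow when recall differs between conditions (9 against 6 words in the examples) and clustering is weak to moderate. Equal recall creates no false strategy effect, although a true effect still shrinks. Loss of many patients follows only if incomplete cases are dropped and clustering is not strong. The results assume per-list scoring and the stated ranges of recall and clustering. The correct recall rate is untouched, but the organization half of the study's aim rests on ARC alone.

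**What to change.** In section 2.5, delete the sentence "For that reason, negative scores were excluded from analyses" and put in its place:

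> All computable ARC scores, including negative values, will be analysed; only a mathematically undefined ARC is treated as missing. The numbers of negative and of undefined scores will be reported by arm, learning strategy and test time.

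Reword the preceding sentence to say that a negative value means less clustering than expected by chance. The analysis without negative scores may be shown as a labelled sensitivity analysis. A mixed model that keeps patients with a missing cell is optional.

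The count of undefined scores matters because ARC becomes 0/0 when every recalled word comes from one category (E = maxR = N − 1), which is itself extreme clustering. This is rare at chance, about 0.1% at 5 words. It reached 33% at 5 words in a simulation where strong clustering also governed which words were recalled, and cannot occur at 6 or more words because each category has only 5.

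The cost is wording only, with no new data; the Study Status section shows recruitment had not begun. Mean ARC will look lower than in work that dropped negative scores, so comparison with such work needs the sensitivity analysis.

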#### 2. Methods

#### 2.1 Participants

60 schizophrenic patients plan to be recruited from the mental health center. All patients must sign an informed consent form.

Patients with schizophrenia are diagnosed and assessed by two chief psychiatrists. Neuropsychological background tests included the Montreal Cognitive Assessment (MoCA)[11] for general cognitive function and the Positive and Negative Syndrome Scale (PANSS)[12]. A parallel-group, single-blind study design was used to assign subjects to the two stimulus types using a stratified randomization method based on baseline Montreal Cognitive Assessment performance. The characteristics of the participants are presented in Table 1, showing no significant differences in participant characteristics between the two stimulation types groups.

Patients with schizophrenia were included based on the following criteria: (1) meeting the diagnostic criteria for schizophrenia according to the Diagnostic and Statistical Manual of Mental Disorders, Fifth Edition (DSM-5); (2) aged 18 years or older, regardless of gender, with an educational level of elementary school or above; (3) all patients received stable-level antipsychotic medication treatment, were in a stable phase of disease treatment, able to understand the testing requirements, and cooperated to complete all research tasks; (4) no history of neurological disorders or other serious physical illnesses, and no history of intellectual disability; (5) no color blindness, color weakness, or other color vision impairments, with normal vision or corrected vision.

Exclusion criteria were as follows: (1) clear cognitive impairment caused by somatic or cerebral organic lesions, such as cerebrovascular diseases, traumatic brain injury, etc; (2) individuals with mental disorders caused by substance dependence or abuse, or the use of psychoactive substances; (3) history of brain injury or other central nervous system-related organic diseases; (4) individuals at significant risk of suicide or harming others; (5) participation in similar experiments in the past 30 days prior to baseline.

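### Allocation is stratified on baseline MoCA but the stated ANOVA has no MoCA term, so the between-arm stimulation test gives up power if MoCA predicts recall

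*Protocol*

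**What the plan says.** Section 2.1 plans a total of 60 patients ("60 schizophrenic patients plan to be recruited from the mental health center") and says the trial will "assign subjects to the two stimulus types using a stratified randomization method based on baseline Montreal Cognitive Assessment performance". It gives no number of strata, cut-points, block size or allocation ratio.

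Section 2.2 sets out a 3 × 2 × 2 design: "Stimulation type was a between-subjects variable, while learning strategy and testing time were within-subject variables". The outcomes are also fixed there: "The dependent variables were the correct recall rate and Adjusted Ratio of Clustering (ARC) scores in the testing phase".

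Section 2.5 names the analysis: "A mixed-design analysis of variance (ANOVA) was conducted to compare the correct recall rates and ARC clustering scores". It describes the comparison to be made as one "between the two learning strategies under two stimulation conditions". It sets a 0.05 significance level, Bonferroni-adjusted post-hoc comparisons and partial eta-squared as the effect size. Neither section includes MoCA as a factor or covariate, and the protocol describes no MoCA-adjusted or sensitivity analysis elsewhere.

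**The concern.** A variable used to stratify allocation should normally also be in the model. Stratifying makes the arms alike on MoCA, so the arm difference varies less from one randomisation to the next. An ANOVA that ignores MoCA does not see this. It leaves the MoCA-related spread between patients in its error term, so the standard error is too large for the design actually used. If MoCA is related to recall, the test rejects less often than its nominal 5% under the null and has less power under the alternative.

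This matters for stimulation in particular. It is the only between-subject factor, so its main effect and the contrasts between arms carry all the patient-to-patient variation, with about 20 patients per arm if there are three equal arms. Learning strategy, retention interval and their interactions with stimulation are tested on within-subject error and are not affected in this way.

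**Working it through.** **Inputs from the protocol.** Total N = 60 (section 2.1); alpha = 0.05 (section 2.5); stratified allocation on MoCA (section 2.1). The arm count is three in section 2.2 but two in sections 2.1 and 2.5, so both were run. The protocol gives no effect size, SD or power, so there is no stated power figure to reproduce.

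**Assumptions, not in the protocol.** Correlation r of MoCA with a patient's mean recall from 0 to 0.6; equal arms, balanced within strata; 2 or 4 strata; active arms 0.8 SD above sham; additive MoCA effect.

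**Step 1: error variance.** With a MoCA term, the between-subject error variance is multiplied by 1 − r². The equivalent gain in sample size is 1/(1 − r²).

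| r | 1 − r² | 1/(1 − r²) |
|---|---|---|
| 0 | 1.00 | 1.00 |
| 0.3 | 0.91 | 1.10 |
| 0.5 | 0.75 | 1.33 |
| 0.6 | 0.64 | 1.56 |

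**Step 2: size of the unadjusted test in the limit of perfect MoCA balance.** With three arms the error degrees of freedom are 60 − 3 = 57. The 5% critical value is F(2, 57) = 3.159. Under the null the unadjusted F is then roughly (1 − r²) times a true F, so its size is about P{F(2, 57) > 3.159/(1 − r²)}. With 2 numerator degrees of freedom, P(F > f) = (1 + 2f/57)^(−28.5).

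- r = 0.3: f = 3.159/0.91 = 3.471, size 3.8%
- r = 0.5: f = 3.159/0.75 = 4.212, size 2.0%
- r = 0.6: f = 3.159/0.64 = 4.936, size 1.1%

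**Step 3: simulation.** 6000 runs, N = 60, balanced permutation within MoCA strata. The patient-mean score was analysed by ANOVA and by ANCOVA with MoCA; this is the between-subject part of the mixed model. Simulation standard error is about √(0.05 × 0.95/6000) = 0.3 points for type I error and √(0.72 × 0.28/6000) = 0.6 points for power.

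| Arms, strata | r | Type I, no MoCA | Power, no MoCA | Power, with MoCA |
|---|---|---|---|---|
| 3, 2 | 0 | 5.2% | 72.9% | 72.6% |
| 3, 2 | 0.3 | 4.0% | 71.1% | 75.0% |
| 3, 2 | 0.5 | 2.9% | 72.1% | 83.1% |
| 3, 2 | 0.6 | 2.0% | 72.6% | 89.6% |
| 3, 4 | 0 | 5.5% | 71.5% | 71.3% |
| 3, 4 | 0.3 | 4.1% | 72.2% | 76.1% |
| 3, 4 | 0.5 | 2.0% | 73.2% | 84.6% |
| 3, 4 | 0.6 | 1.3% | 73.0% | 90.0% |

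At r = 0.1 with three arms, power is 72–73% with or without MoCA. With three arms and two strata, the adjusted test keeps its size (4.5–5.1%). The four-strata type I figures lie close to the limit in step 2.

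With two arms of 30, power without and with MoCA is 86% and 86% at r = 0, 87% and 89% at r = 0.3, 88–89% and 94% at r = 0.5, and 89–90% and 96–97% at r = 0.6.

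**Step 4: a single contrast.** The normal-approximation power for two arms of 20 at 0.8 SD, two-sided 5%, is 71.6%. Multiplying the SD by √(1 − r²) gives 75.6% at r = 0.3 and 83.2% at r = 0.5, in line with the simulation.

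**Step 5: the interaction.** For stimulation by strategy (retrieval minus restudy difference; three arms, four strata; effect 0.8 SD of that difference), power is 73.1%, 72.3%, 72.8% and 72.1% without MoCA at r = 0, 0.3, 0.5 and 0.6. With MoCA it is 72.9%, 71.9%, 72.1% and 72.0%. There is no gain.

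**The case against.** **The model sentence may be only a summary.** Section 2.5 does not mention retention interval, although section 2.2 makes it a design factor, and covariates are often left to a statistical analysis plan, which is not shown here. This has some weight. However, sections 2.2 and 2.5 together give the test, every factor, the significance level, the multiplicity correction and the effect measure. A later plan that added MoCA would change the model written here.

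**Conservatism needs balance within strata.** Section 2.1 gives no blocking. With unrestricted randomisation (three arms, 4000 runs) the unadjusted type I error is 5.0%, 5.0% and 5.2% at r = 0.3, 0.5 and 0.6, so the test is not conservative. That is not the stratified allocation the protocol describes, but the low type I figures do rest on the strata achieving balance. The power gain does not depend on it: under unrestricted randomisation, power rises from 69.8% to 73.7%, 70.8% to 82.6% and 70.4% to 87.8%.

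**The stated aim is barely touched.** The introduction asks "whether combining tDCS, tACS with retrieval practice facilitates the maintenance of semantic memory", which is closest to the stimulation by strategy interaction, and that test gains nothing. This stands and limits the point. The introduction also plans a comparison of active with sham stimulation, and there the gain applies.

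**The size is assumed.** This also stands. No passage gives the MoCA–recall correlation; at r = 0.1 there is no gain, and at r = 0.3 only about 2 to 4 points. Nothing was computed for ARC or for the Bonferroni-adjusted contrasts.

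**Conclusion.** The point holds as a loss of efficiency, not an error of validity. The protocol controls MoCA at allocation and then states a model that ignores it. If MoCA predicts recall, the stimulation main effect and the arm contrasts are tested with more error than necessary. Under the assumptions listed, with three arms, power is lower by about 4 points at r = 0.3, 11 at r = 0.5 and 17 at r = 0.6. With two arms the loss is about 2, 5 to 6, and 6 to 8 points. At r = 0 to 0.1 nothing material is lost.

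The figures are for recall. The MoCA–ARC correlation is also not given, and section 2.5 removes negative ARC scores, which changes the number analysed. Confidence is medium, because the correlation is unknown and a separate analysis plan could already add the term.

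**What to change.** Pre-specify baseline MoCA as a continuous, mean-centred covariate in the mixed models for recall rate and ARC, and report MoCA-adjusted differences between arms. Centring keeps the strategy and interval main effects interpretable. Keep the stimulation by strategy interaction as a within-subject test and claim no precision gain for it.

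The cost is one between-subject degree of freedom (57 to 56 with three arms). The MoCA score is already needed for allocation, so no extra data are collected. If MoCA turns out to be unrelated to recall, the simulated loss of power is 0.3 points or less (72.9% to 72.6% at most in the table). The protocol's study status is not yet recruiting, so the term can be fixed before any data exist; added later, it would be post hoc.
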